7.3. MISSING DATA

Missing efficacy data will be handled as described in section 15.1.2 of this analysis plan.

Missing safety data will be subject to LOCF analysis as specified in relevant safety domain sections.

7.4. MULTIPLE COMPARISONS/ MULTIPLICITY

An analysis must be conducted taking into account the multiple dose regimens for primary efficacy analysis, as there are 2 active treatment groups being compared to a single placebo treatment group.

Type I error for rejection of the null hypothesis (see section 15.1.3) will be controlled at $\alpha=0.05$ (two-sided) using the Hochberg procedure (Hochberg, 1988).

The hypotheses being tested are:

- $H_{0(1)}$: $\mu_{20-60} = \mu_{\text{placebo}}$ versus the alternate H_{11} : $\mu_{20-60} \neq \mu_{\text{placebo}}$.
- $H_{0(2)}$: $\mu_{80-120} = \mu_{\text{placebo}}$ versus the alternate H_{12} : $\mu_{80-120} \neq \mu_{\text{placebo}}$.

Let p_{20} and p_{80} denote the p-values for the two primary comparisons on the primary efficacy parameter; then define $p_{\min} = \min(p_{20}, p_{80})$, and $p_{\max} = \max(p_{20}, p_{80})$, representing the two dosing regimens being evaluated. Within the Hochberg multiple comparison procedure one of the following three cases will apply:

- If $p_{\max} \leq 0.050$ then both primary tests are classified as statistically significant;
- If $p_{\max} > 0.050$ and $p_{\min} \leq 0.025$ then the test corresponding to p_{\min} is classified as statistically significant, and the test corresponding to p_{\max} is classified as not statistically significant; or
- If $p_{\max} > 0.050$ and $p_{\min} > 0.025$ then both primary tests are classified as not statistically significant.

In summary, if both tests have $p \leq 0.05$, then both null hypotheses are rejected; if the less significant test (p_{\max}) has $p \geq 0.05$, then that null hypothesis ($H_{0(2)}$) is not rejected, and the other null hypothesis ($H_{0(1)}$) is tested at the 0.025 level.

This analysis will be conducted using the MULTTEST procedure in SAS.

7.5. EXAMINATION OF SUBGROUPS

Subgroup analyses will be conducted on change from baseline results for MADRS total score and CGI-BP-S depression score from Week 1 to Week 6, including Week 6 (LOCF) endpoint. It should be noted that the study was not designed to detect treatment differences with high statistical power within subgroups.

The efficacy analyses to be repeated on subgroups are the MMRM and ANCOVA methods for both MADRS and CGI-BP-S. This analysis will only be performed on the ITT population. Additionally, SDS, HAM-A and YMRS will be analyzed separately by country.

A subgroup analysis will also be performed upon a selection of safety parameters. These parameters are DIEPSS

Document:	K:\DSP\SM-13496\KVA95374\Biostatistics\Documentation\SAP		
Author:	[REDACTED]	Version Number:	1.0
		Version Date:	30MAR2017

Template No: CS_TP_BS016 -- Revision 3

Reference: CS_WI_BS005

Effective Date: 01May2012

Copyright © 2012 [REDACTED] All rights reserved.

The contents of this document are confidential and proprietary to [REDACTED]. Unauthorized use, disclosure or reproduction is strictly prohibited.

(ANCOVA only) as well as weight, BMI, QTc, and selected laboratory parameters (ANCOVA only). A small number of specified Adverse Event tables will also be split by subgroup. Safety parameter subgroup analyses will be performed on the Safety population.

The full analysis methods for subgroups are detailed in section 15.2.4.

The following subgroups will be assessed and described within the exploratory analysis sections:

- Sex:
 - Male
 - Female
- Age (years):
 - <55
 - ≥55
 - And
 - <65
 - ≥65
- Bipolar I Diagnosis Subtype (Efficacy Analyses only)
 - Rapid Cycling
 - Non-rapid Cycling
- Country
 - Japan
 - Ukraine
 - Philippines
 - Taiwan
 - Russia
 - Malaysia
 - Lithuania
 - Slovakia

8. OUTPUT PRESENTATIONS

Appendix 1 shows conventions for presentation of data in outputs.

The templates provided with this SAP describe the presentations for this study and therefore the format and content of the summary tables, figures and listings to be provided by [REDACTED]

Summaries for categorical data will include frequency counts and percentages. For continuous data points, summaries will include a count, mean, standard deviation, median, minimum and maximum.

Document: K:\DSP\SM-13496\KVA95374\Biostatistics\Documentation\SAP
Author: [REDACTED] Version Number: 1.0
Version Date: 30MAR2017

Template No: CS_TP_BS016 – Revision 3
Effective Date: 01May2012

Reference: CS_WI_BS005

Copyright © 2012 [REDACTED] All rights reserved.
The contents of this document are confidential and proprietary to [REDACTED] authorized use, disclosure or reproduction is strictly prohibited.

9. DISPOSITION AND WITHDRAWALS

All patients who provide informed consent and are screened will be accounted for in this study.

Subject disposition and withdrawals will be presented for all enrolled patients. Protocol violations (as defined in section 5.2), including inclusion and exclusion criteria, will be presented for the ITT population. Number of patients screened, randomized, completed, discontinued and continuing into the extension study will be summarized, along with reasons for discontinuation as required.

This summary will be repeated separated by country.

10. DEMOGRAPHIC AND OTHER BASELINE CHARACTERISTICS

Demographic data and other baseline characteristics will be presented for the ITT population, safety population and PP population. This summary will be repeated separated by country for the ITT population.

No statistical testing will be carried out for demographic or other baseline characteristics.

The following demographic and other baseline characteristics will be summarized and listed for this study. Data points denoted by * are reported in a listing only:

1) Demographics

- Age
- Sex
- Race
- Ethnicity
- Height
- Country
- Weight
- BMI

2) Disease data

- Date of initial onset of bipolar I disorder
- DSM-IV-TR diagnostic code (regarding severity/psychotic/remission specifiers) of the current major depressive episode or other current episode
- Date of onset of the current major depressive episode
- Presence or absence of characteristics of rapid cycling disease course
- Number of mood episodes for the consequent 12 months, by episode type

Document: K:\DSP\SM-13496\KVA95374\Biostatistics\Documentation\SAP

Author: [REDACTED]

Version Number:

1.0

Version Date:

30MAR2017

Template No: CS_TP_BS016 – Revision 3

Reference: CS_WI_BS005

Effective Date: 01May2012

Copyright © 2012 [REDACTED] All rights reserved.

The contents of this document are confidential and proprietary to [REDACTED]. Unauthorized use, disclosure or reproduction is strictly prohibited.

- Date of onset of the most recent manic episode, hypomanic episode, and mixed episode*
- Date of most recent hospital discharge if hospitalized because of manic, mixed manic or depressive episodes*
- Number of hospitalizations due to bipolar I disorder
- Psychiatric disease other than bipolar I disorder; diagnosis, DSM-IV-TR diagnostic code, date of onset*
- Baseline scores for MADRS, CGI-BP-S and SDS.

3) Bipolarity Index (BPI)*

The BPI is a diagnostic instrument that considers 5 "dimensions" of bipolarity:

1. Hypomania or mania
2. Age of onset of first mood symptoms
3. Illness course and other features generally only apparent over time
4. Response to medications (antidepressants and mood stabilizers)
5. Family history of mood and substance use problems

11. SURGICAL AND MEDICAL HISTORY

Medical History information will be presented for the ITT population and the SAF population.

- Medical History will be coded using **MedDRA Version 19.1**
 - o Medical History conditions are defined as those conditions beginning prior to screening which stop prior to/are ongoing at Screening.
 - o Summarized by System Organ Class (SOC) and Preferred Term (PT).

12. CONCOMITANT MEDICATIONS

Concomitant Medications will be presented for the Safety population and coded using **WHO Drug Dictionary Enhanced /WHO Herbal Dictionary v01DEC2013**.

ATC coding will be performed for the study, including screen failed patients. Medications will be summarized using ATC level 3 coding and Preferred Term.

See Appendix 2 for handling of partial dates for medications, in the case where it is not possible to define a medication as prior, concomitant, or post treatment, the medication will be classified as both prior and concomitant.

- 'Prior' medications are medications which started prior to the first dose of study medication. If they are ongoing at start of dosing then the medication will be classified as both prior and concomitant.
- Concomitant' medications are medications which:

Document: K:\DSP\SM-13496\KVA95374\Biostatistics\Documentation\SAP
Author: [REDACTED] Version Number: 1.0
Version Date: 30MAR2017

Template No: CS_TP_BS016 – Revision 3
Effective Date: 01May2012

Reference: CS_WI_BS005

Copyright © 2012 [REDACTED] All rights reserved.
The contents of this document are confidential and proprietary to [REDACTED]. Unauthorized use, disclosure or reproduction is strictly prohibited.

- o started prior to, on or after the first dose of study medication and started no later than one day before the end of the double blind phase
- o AND ended on or after the date of first dose of study medication or were ongoing at the end of the study.
- 'Post' medications are medications which started on the same day, or after the end of study treatment for patients who are not continuing into the extension study. For patients continuing into the extension study, the medication should be captured in the extension study database.

A summary of patients with concomitant use of antiparkinson medication will be summarized by treatment group. An additional summary will be produced categorizing medication categories related to Anxiolytics and Hypnotics.

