4.3.2 Procedures for discontinuation

When a patient who enters the treatment phase discontinues before study completion, the investigator should perform all applicable activities scheduled at the time of discontinuation and the follow-up assessment, and record the primary reason in the electronic case report form (eCRF). The investigator will access the IWRS and update the patient final status. The date of discontinuation is defined as the day of final administration of the study drug. The study drug unused or partially used should be returned by the patient.

If a patient discontinues the study treatment because of any AEs, the patient should be monitored until resolution or stabilization of the AE, and the investigator should perform the best possible observation, tests and evaluation as well as give appropriate treatment and take all possible measures for the safety of the patient. Any AEs that are present at the time of discontinuation/withdrawal should be followed in accordance with the safety requirements outlined in Section 6.4.1.4 (see Page 54).

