5.2 Treatment

5.2.1 Dosage of the study drug

The study drug administration will be initiated on the day after randomization. Patients in the 20-60 mg group will receive 20 mg of SM-13496 on Days 1 to 7 and then flexible dose of SM-13496 within a range of 20 to 60 mg for 5 weeks (starting on Day 8). Patients in the 80-120 mg group will receive 20 mg of SM-13496 on Days 1 and 2, 40 mg on Days 3 and 4, 60 mg on Days 5 and 6, 80 mg on Day 7, and then flexible dose within a range of 80 to 120 mg for 5 weeks (starting on Day 8). Patients in the placebo group will receive placebo for 6 weeks. The study drug should be administered orally within 30 minutes after evening meal once daily.

The dose can be increased or decreased by 20 mg/day at the scheduled visits from Week 1 to 5. At the scheduled visits at Week 1 or after, when no safety concerns are found and the CGI-BP-S (depression) score is within the range from 5 (markedly ill) to 7 (very severely ill), the dose should in principle be increased by 20 mg/day. When any safety concerns are raised, the dose can be reduced by 20 mg/day at unscheduled visits. Dose increases will be not permitted at unscheduled visits. At all visits after Visit 2 (Day -1, baseline), including unscheduled visits, the reason for the dose selection should be stated in the electronic case report forms (eCRFs).

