5.3.2 Restricted concomitant medications/therapies

5.3.2.1 Psychotropic medications

(1) Psychotropic medications (excluding antiparkinson drugs, anxiolytics, and hypnotics)

Psychotropic medications (eg, antipsychotics, antidepressants, mood stabilizers) excluding permitted antiparkinson drugs, anxiolytics, and hypnotics (see Items (2) to (4) in this section) will be restricted as follows:

- For patients untreated with psychotropic medication at screening, psychotropic medications will be prohibited from screening until the end of the treatment phase.
- For patients treated with any psychotropic medications at screening, the psychotropic medications should be titrated down appropriately and terminated at least 3 days before the initiation of the study treatment. Psychotropic medications will be prohibited during the treatment phase.

(2) Medications for extrapyramidal symptoms (eg, antiparkinson drugs)

Medications for extrapyramidal symptoms (eg, antiparkinson drugs) will be restricted as follows:

- For patients untreated with drugs for extrapyramidal symptoms at screening, drugs for extrapyramidal symptoms will be prohibited from screening until the initiation of the study treatment.
- For patients treated with drugs for extrapyramidal symptoms at screening, the drugs should be titrated down appropriately and terminated before the initiation of the study treatment.
- For all patients, if any extrapyramidal symptoms develop or worsen after the initiation of the study treatment, only one of the drugs listed in Table 4 may be used, within the dose range specified in the table. If the drug is not effective, the drug may be replaced by another drug among the drugs listed in Table 4. For akathisia, propranolol (≤ 120 mg/day), amantadine (≤ 300 mg/day), or one of the drugs listed in Table 4 may be used. If the above-mentioned drugs are not available at the study site, similar drugs at equivalent doses may be used with prior authorization of the medical monitor.
- For all patients, antiparkinson drugs and other drugs for extrapyramidal symptoms will be prohibited for prophylactic purposes.

Table 4 Permitted concomitant antiparkinson drugs

Drug	Daily dose
Biperiden	≤ 16 mg
Trihexyphenidyl	≤ 10 mg
Benztropine	≤ 6 mg
Diphenhydramine	≤ 300 mg

(3) Anxiolytics

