9.7.5 Concomitant medications

Number and percentage of patients with concomitant use of antiparkinson medication will be summarized by treatment group.

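### The SAP's cut-off for concomitant medication can drop an antiparkinson drug first started on the day of the last double-blind dose, or place it in two classes

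*SAP*

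**What the plan says.** SAP Section 12 sets two conditions for a concomitant medication. It must have "started no later than one day before the end of the double blind phase", and it must have ended on or after the first dose date or still be ongoing at study end. The Post class consists of "medications which started on the same day, or after the end of study treatment for patients who are not continuing into the extension study". If a patient does continue, the SAP refers the medication to the extension study's database. The phase end and the treatment end are different terms, and Section 12 ties neither to a date.

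The antiparkinson summary in Section 12 is of concomitant use, so this definition governs it. It implements a safety variable named in Protocol 3.4.3 and under secondary objective 5. Protocol 9.7.5 states the analysis: "Number and percentage of patients with concomitant use of antiparkinson medication will be summarized by treatment group". The protocol does not exclude the last dosing day, and SAP 3.3 reports no change from the protocol analyses.

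Four other provisions bear on that day:

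- Protocol 5.2.1: "The study drug should be administered orally within 30 minutes after evening meal once daily".
- Protocol 4.3.2: "The date of discontinuation is defined as the day of final administration of the study drug".
- Protocol 5.3 records all medication in this study's eCRF up to the Visit 8 assessment (continuing patients) or the follow-up visit (others).
- SAP 13.1 computes exposure as last minus first dose date plus 1. SAP 16.1 counts adverse events as treatment-emergent through the last double-blind dose date for continuing patients, and to 7 days after stopping for the others.

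**The concern.** A patient may develop akathisia or rigidity on the last dosing day and start an antiparkinson drug that day. The plan treats the day as exposure and the event as treatment-emergent. If the phase ends on the last-dose date, the same plan does not count the drug given for that event as concomitant. In a non-continuing patient it becomes Post. In a continuing patient it falls outside this study's classes, although this study's eCRF holds the record and no extension dose has been taken.

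At stake is a descriptive proportion, but a pre-specified one that addresses an expected side effect of the drug class. The patients most exposed to the rule are those whose extrapyramidal symptoms lead to treatment and stopping on the same day. Their number could differ between arms. Because the end date is undefined, two programmers could also report different rates from the same data.

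**Working it through.** **1. Date rules.** The plan states no figure to reproduce, so the rules themselves are applied. Let D be the last-dose day and E the end of the double-blind phase. Take D = 42 for illustration and treat the end of study treatment as D. Then:

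- concomitant if start ≤ E − 1 (the stop-date condition is assumed met);
- Post if start ≥ D and the patient does not continue.

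E = 42 places the phase end on the last dose. E = 43 or 45 places it at Visit 8, which may be held up to 72 hours after the last dose.

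| E | Patient | Start Day 41 | Start Day 42 (last dose) | Start Day 43 |
|---|---|---|---|---|
| 42 | Not continuing | Concomitant | Post only | Post only |
| 42 | Continuing | Concomitant | Neither (extension database) | Neither (extension database) |
| 43 | Not continuing | Concomitant | Concomitant and Post | Post only |
| 43 | Continuing | Concomitant | Concomitant | Neither (extension database) |
| 45 | Not continuing | Concomitant | Concomitant and Post | Concomitant and Post |
| 45 | Continuing | Concomitant | Concomitant | Concomitant |

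For non-continuing patients the two rules meet without gap or overlap only when E = D. That makes the last-dose reading the natural one of the pair, but the SAP does not state it.

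**2. Who is at risk.** Only first starts on Day D are affected. A drug started earlier and still in use stays concomitant under every reading. Protocol 5.3.2.1 requires earlier drugs for extrapyramidal symptoms to be stopped before study treatment begins, so a patient using one during treatment should be a new starter.

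**3. Size when E = D.** Patients lost per arm = 167 × r × s. Here 167 is the target per arm (Protocol 3.5), r is the true proportion using antiparkinson drugs, and s is the share of first starts that fall on Day D. The documents give neither r nor s, so both are assumptions. Evenly spread starts over 42 days give s = 1/42 = 2.4%.

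| r | s = 1/42 | s = 5% | s = 10% |
|---|---|---|---|
| 5% | 0.20 (0.12 points) | 0.42 (0.25) | 0.83 (0.5) |
| 10% | 0.40 (0.24) | 0.83 (0.5) | 1.67 (1.0) |
| 20% | 0.80 (0.48) | 1.67 (1.0) | 3.34 (2.0) |

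Cells show patients lost per arm, with percentage points of the arm (100 × r × s) in brackets. Relative to true users, the fraction lost is s itself.

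**The case against.** The strongest reply is that the loss depends on one reading of an undefined term. Section 12 uses two different anchors, and the schedule in Protocol Table 1 places the Week 6 visit inside the double-blind treatment phase. With evening dosing, the last dose will often be the evening before Visit 8. On the Visit 8 reading, a drug started that evening is therefore concomitant and the patient is counted. The double class is then only untidy, and Section 12 already lets a drug be both prior and concomitant. This stands: an undercount is not certain. It does not remove the need for a defined date, because the SAP does not choose between the readings.

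A second reply is that a patient who is stopped and treated at a daytime visit usually took the last dose the evening before. Post is then correct. This also stands and narrows the group at risk.

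A third is that extrapyramidal effects are also captured by adverse events and the DIEPSS, and the drug remains on record. That limits the consequence but does not make the proportion right.

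A reader might infer more than the documents support:

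- *Drugs taken just before the Week 6 rating escape a check.* The SAP specifies no such check. Its anxiolytic and hypnotic summary is affected only if it uses the concomitant flag.
- *The per-protocol population is affected.* SAP 5.2 words that criterion by the treatment phase and applies it through medical review, not through this flag. It also exempts antiparkinson drugs, anxiolytics and hypnotics.
- *Leaving out propranolol for akathisia is a second undercount.* The protocol variable is antiparkinson use, and the SAP follows it. Widening it would redefine a protocol variable.

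**Conclusion.** The concern holds in a limited form. The end date in Section 12 is undefined. On the reading that makes its rules fit together, a first antiparkinson drug started on the last-dose day is lost from a named safety variable. That is at odds with the plan's own exposure, adverse-event and recording rules. On the Visit 8 reading, the fault is overlapping classes in non-continuing patients, with no undercount.

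The expected size is small: about 0.2 to 0.8 patients per arm with even starts and assumed use of 5% to 20%, and about 0.8 to 3.3 if 10% of starts fall on that day. The loss could differ by arm where symptoms lead to treatment and stopping on the same day. It would be tempting to conclude that the rule biases the comparison in favour of active drug. The documents give no rates by arm and no timing of starts, so that remains a possibility, not a finding. The primary MADRS analysis does not use the concomitant flag.

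**What to change.** In SAP Section 12, define a concomitant medication as one that started on or before the date of the last double-blind dose, and that ended on or after the first dose date or was ongoing. Define Post as started after the last double-blind dose date. Apply both to continuing and non-continuing patients. The two classes are then mutually exclusive, and the cut-off matches the adverse-event window for continuing patients. For the others that window still runs 7 days longer, so a drug first started in those days remains Post.

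The cost is a change of a sentence or two and one derived flag. Start and stop dates are already on the eCRF. The downside is that the reported user rate may rise slightly.

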13. STUDY MEDICATION EXPOSURE

Exposure to study medication in days will be presented for the ITT population and SAF population.

The date of first and last study medication administration will be taken from the eCRF drug administration and accountability form. Return of the blister card at any given visit is not a prerequisite for inclusion in exposure summary statistics if corresponding dose start and end dates are reported.

Interruptions, compliance, and dose changes are not taken into account for duration of exposure.

The average daily assigned dose will be summarized for the Safety and ITT populations by treatment group stratified for all patients and completers. The modal daily assigned dose will likewise be summarized based on overall study drug exposure; if there is more than one modal daily assigned dose for a subject, the last modal assigned dose administered will be used in the overall summary. Return of the blister card at any given visit is not a prerequisite for inclusion in average daily assigned dose summary statistics or modal daily assigned dose summary statistics if corresponding dose start and end dates are reported. For the purpose of computing average daily dose and modal daily dose (overall), dose level will be imputed during Week 1 for patients randomized to the 80-120 mg treatment arm because dose titration was required for this group during this week (see Protocol Section 3.3), and will be based on the assumption that dosing instructions associated with titration have been followed correctly (i.e. 20 mg tablets taken on Days 1-2, 40 mg tablets taken on Days 3-4, 60 mg tablets taken on Days 5-6, and 80 mg tablets taken on Day 7).

The number of subjects receiving each dose within a given study week will be presented. A summary of dose change from previous scheduled visit will be presented by assigned dose level for patients in the Safety and ITT populations. Return of the blister card at any given visit is not a prerequisite for inclusion in dose change summary statistics if corresponding dose start and end dates are reported.

